2.2 B Newly Diagnosed AML in Older Patients

AML is primarily a disease of older people with a median age of diagnosis of 68 years. There are approximately 13,000 new cases of AML per year in the United States and 55% of these occur in individuals who are age 65 years and older. AML in older patients is phenotypically different from AML in younger patients. As compared to their younger counterparts, older patients with AML more frequently have an antecedent hematological disorder or unfavorable cytogenetics, and respond less well to chemotherapy

Elderly patients with AML have a poor prognosis, which is attributed to having disease that is inherently more resistant to current standard cytotoxic agents and/or relatively poor tolerance of these agents because of comorbidity and reduced tolerance of adverse effects. As a result, despite steady progress in the therapy of AML in younger patients, treatment for elderly patients with AML has not improved for decades. Among patients 70 years or older and those with adverse karyotypes the 4-8 week mortality with intensive chemotherapy is 30%-50%, and the median survival is 4-7 months. Therefore such patients derive little benefit from intensive chemotherapy, and some may in fact be harmed with intensive chemotherapy. Such high induction mortality rates and poor tolerance to chemotherapy have resulted in a reluctance to treat AML in older patients. A Surveillance Epidemiology and End Results database analysis has indicated that 64% of AML patients over age 65 receive no therapy for AML, other than supportive care. This untreated group has a dismal median survival of 1.7 months.

Hypomethylating agents are the most frequently used agents in the treatment of less fit, older patients with AML in the US and Europe. The DAGO-016 study compared the efficacy and safety of decitabine ($20\text{ mg}/\text{m}^2/\text{day}$ for 5 days every 4 weeks) versus treatment of choice (TC) (including LDAC $20\text{ mg}/\text{m}^2/\text{day}$ for 10 days every 4 weeks or best supportive care) in 485 patients with AML (median age 73 years) ineligible for cytotoxic chemotherapy (Kantarjian et al., JCO 2012; Thomas X et al., CLML 2014). The CR rate plus CRp was 17.8% with decitabine versus 7.8% with TC (odds ratio, 2.5; $P = .001$). The initial analysis showed a trend toward improved survival with decitabine (7.7 vs. 5.0

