months; $P = 0.108$) that became significant ($P = 0.037$) with further follow-up. Azacitidine has shown benefit in elderly patients with AML in two large multicenter trials. In one trial patients with AML with 20–30% blasts were evaluated as a subset analysis of the phase III

AZA-001 trial (Fenaux et al., JCO 2010). The patients were randomly assigned to receive subcutaneous azacitidine or conventional care regimen CCR (best supportive care [BSC] only, low-dose cytarabine (LDAC), or intensive chemotherapy [IC]). The morphologic CR rate was 18% (10 of 55 patients) in the azacitidine group and 16% (nine of 58 patients) in the CCR group ($P = .80$). At a median follow-up of 20.1 months, the median OS for azacitidine-treated patients was 24.5 months compared with 16.0 months for CCR-treated patients ($P = 0.005$), and 2-year OS rates were 50% and 16%, respectively ($P = 0.001$). In another trial, 488 elderly patient's with AML with >30% blasts and age ≥ 65 years were randomized to receive either azacitidine (75 mg/m²/day for 7 days every 4 weeks) or a CCR (standard induction chemotherapy, LDAC, or supportive care only) (Dombret et al., Blood 2015). Overall response (CR + CRi) rates were comparable in the azacitidine (27.8%) and CCR (25.1%) arms ($P = .5384$). Median OS was 10.4 months (1-year survival 47%) for patients receiving azacitidine compared to 6.5 months (1-year survival 34%) for patients receiving CCR ($P = 0.0829$). A prespecified analysis censoring patients who received AML treatment after discontinuing study drug showed median OS with azacitidine vs CCR was 12.1 months vs 6.9 months (stratified log-rank $P = .0190$). The dismal prognosis in elderly AML patients has resulted in increased efforts and clinical trials to improve the frontline therapy in elderly patients (≥ 60 years) with AML.

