11.2 Sample Size

Arm 1:***Part a. Lead-in phase***

The primary objective of the lead-in phase is to determine the safety of nivolumab in combination with 5-azacytidine in patients with refractory/ relapsed AML. Up to 30 patients will be accrued into the lead-in part of the study.

Part b. Expansion phase

- A. Up to 70 patients (including 6 patients treated at the MTD from the lead-in part) with relapsed/refractory AML will be recruited for the Arm 1 Salvage cohort .
- B. Up to 40 newly diagnosed older AML patients (age ≥ 65) will be recruited for the Arm 1 Frontline older cohort .

Arm 2:**Part a. Lead-in phase**

The primary objective of the lead-in phase is to determine the safety of nivolumab with ipilimumab in combination with 5-azacytidine in patients with refractory/ relapsed AML. Up to 24 patients will be accrued into the lead-in part of the study.

Part b. Expansion phase

- A. Up to 54 patients (including 6 patients treated at the MTD from the lead-in part) with relapsed/refractory AML will be recruited for the Arm 2 Salvage cohort.
- B. Up to 30 newly diagnosed older AML patients (age ≥ 65) will be recruited for the Arm 2 Frontline older cohort.

The efficacy of the combination will be measured by the overall response rate (ORR), defined as CR (complete remission) + CR_p (complete remission with incomplete platelet recovery) + CR_i (complete remission with incomplete count recovery) + PR (partial response) + marrow clearance of blasts + hematologic improvement (HI) in platelets, hemoglobin, or ANC within 3 months of treatment initiation among adult patients with refractory/ relapsed AML AND newly diagnosed older patients with AML. ORR and toxicity will be monitored simultaneously using the Bayesian approach of Thall, Simon, Estey (1995, 1996) and the extension by Thall and Sung (1998).

Arm 3:**Part a. Lead-in phase**

The primary objective of the lead-in phase is to determine the safety of nivolumab with 5-azacytidine and venetoclax in patients with refractory/ relapsed AML. A total of 18 patients (3 dose levels with a maximum of 6 patients at each dose level) will be accrued into the lead-in part of the study.

Part b. Expansion phase

- A. A total of 30 patients (excluding 6 patients treated at the MTD from the lead-in part) with relapsed/refractory AML will be recruited for the Arm 3Salvage cohort.
- B. A total of 30 newly diagnosed older AML patients (age ≥ 65) will be recruited for the Arm 3 Frontline older cohort.

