Once safety of the MTD has been established, any patients still on study at a dose lower than MTD can be dose escalated up to MTD. Patients treated in the lead-in phase at MTD

will be included in the Phase II portion of the study.

The efficacy of the combination will be measured by the overall response rate (ORR), defined as CR (complete remission) + CRp (complete remission with incomplete platelet recovery) + CRi (complete remission with incomplete count recovery) + MLFS within 6 months of treatment initiation among adult patients with refractory/ relapsed AML AND newly diagnosed older patients with AML. ORR and toxicity will be monitored simultaneously using the Bayesian approach of Thall, Simon, Estey (1995, 1996) and the extension by Thall and Sung (1998).

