Multc Lean Desktop (version 2.1.0) was used to generate the toxicity and futility stopping boundaries and the OC table (Table 17). In order to utilize the software for the design, a 15% constant rate and beta(0.3, 1.7) priors were assumed for the standard treatment response distribution and experimental treatment response prior distribution, respectively. In addition, a 30% toxicity constant rate and beta (0.6, 1.4) priors were assumed for the

standard treatment toxicity constant rate and experimental treatment toxicity prior distribution, respectively.

The probability of stopping the study early if the true ORR of the combination treatment was 30% and the true toxicity rate was 30% was 16.9%. Probabilities of stopping early for high true toxicity rates (i.e., 50%) were 93.5% when the true ORR was 30% and 97.8% when true ORR rate was 15%.

Table 17. Operating characteristics for simultaneous monitoring response and toxicity rates for

| True Toxicity Rate | True ORR | Prob(stop the trial early) |
|--------------------|-------------|----------------------------|
| 0.10 | 0.15 | 0.6760 |
| | 0.20 | 0.3539 |
| | 0.25 | 0.1404 |
| | 0.30 | 0.0459 |
| | 0.35 | 0.0136 |
| | 0.40 | 0.0040 |
| 0.20 | 0.15 | 0.6787 |
| | 0.20 | 0.3594 |
| | 0.25 | 0.1477 |
| | 0.30 | 0.0540 |
| | 0.35 | 0.0220 |
| | 0.40 | 0.0124 |
| 0.30 | 0.15 | 0.7179 |
| | 0.20 | 0.4375 |
| | 0.25 | 0.2516 |
| | 0.30 | 0.1694 |
| | 0.35 | 0.1412 |
| | 0.40 | 0.1328 |
| 0.40 | 0.15 | 0.8603 |
| | 0.20 | 0.7214 |
| | 0.25 | 0.6293 |
| | 0.30 | 0.5886 |
| | 0.35 | 0.5747 |
| | 0.40 | 0.5705 |
| 0.50 | 0.15 | 0.9779 |
| | 0.20 | 0.9559 |
| | 0.25 | 0.9414 |
| | 0.30 | 0.9349 |
| | 0.35 | 0.9327 |
| | 0.40 | 0.9321 |

D. Arm 2 Newly diagnosed older AML (≥ 65 years) cohort (Aza+Nivo+Ipi) (N=30)

Historical data on similar patients show an ORR of 18-25% [the historical response rate in older newly diagnosed AML (≥ 65 years) with single agent hypomethylator therapy (5-

Nivolumab and azacytidine

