azacytidine or decitabine) in three large randomized phase II trials was 17.5 % with decitabine alone in patients with AML (Kantarjian et al., JCO 2012), 18% with azacytidine alone in patients with AML and blasts 20-30% (Fenaux et al., JCO 2010), and 27.8% with azacytidine alone in patients with AML and blasts >30% (Dombret et al., Blood 2015)]. The target ORR with the experimental treatment is 40%. This regimen of the Aza+Nivo+Ipi combination treatment will be considered worthy of further investigation if it elicits an increase in ORR to 40% with acceptable toxicity. A >30% drug-related grade 3/4 toxicity rate is considered unacceptable. Thus, interim monitoring rules, assuming the prior distributions below, were constructed that meet the following two conditions,

- 7) Stop if $\text{Prob}\{ p(\text{ORR}, E) < p(\text{ORR}, H) + 0.15 \mid \text{data} \} > 0.99$, or
- 8) Stop if $\text{Prob}\{ p(\text{TOX}, E) > 0.30 \mid \text{data} \} > 0.95$,

where $P(\text{ORR}, E)$ and $P(\text{TOX}, E)$ are the true ORR and toxicity rates for the combination treatment, and $p(\text{ORR}, H)$ is the true ORR rate of the standard treatment. The first rule provides for stopping the study if the data suggest that it is unlikely (i.e., probability < 1%) that ORR rate of the combination treatment is greater than the ORR rate of standard treatment by 15.0%. The second condition will stop the study early if excessive therapy-related grade 3/4 toxicity (>30%) is highly probable (i.e., probability >95.0%) for the combination treatment. Monitoring for toxicity and futility will not begin until 6 patients have been evaluated, and cohort size for future evaluations is 3.

The monitoring rule for the toxicity rate, based on these assumptions and monitoring conditions above is found in Table 18. **For example, accrual will cease if 5 or more patients experience toxicities among the first 6 patients.**

| Table 18. Stop accrual if the number of drug-related grade 3/4 toxicities is greater than or equal to indicated (i.e., # patients with toxicities) among the number of patients evaluated | | | | | | | | | | |
|---|------------------------------------|-----|-----|------|------|------|-------|-------|-------|-------------------------------------|
| # patients evaluated | 3 | 6 | 9 | 12 | 15 | 18 | 21 | 24 | 27 | 30 |
| # patients with toxicities | Never stop with this many patients | 5-6 | 6-9 | 7-12 | 8-15 | 9-18 | 11-21 | 12-24 | 13-27 | Always stop with this many patients |

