Monitoring the ORR rate, based on the above assumptions and monitoring conditions is found in Table 19. **For example, accrual will cease if no patient experience an overall response within 3 months of initiation of therapy in the first 8 patients treated.**

| Table 19. Stop accrual if the number with overall response is less than or equal to indicated (i.e., # patients with overall response) | | | | | | | | |
|--|------------------------------------|-----|----|-------|----|----|----|-------------------------------------|
| # patients | 3 | 6-9 | 12 | 15-18 | 21 | 24 | 27 | 30 |
| # patients with overall response | Never stop with this many patients | 0 | 1 | 2 | 3 | 4 | 5 | Always stop with this many patients |

Multc Lean Desktop (version 2.1.0) was used to generate the toxicity and futility stopping boundaries and the OC table (Table 19). In order to utilize the software for the design, a 25% constant rate, and beta(0.5,1.5) priors were assumed for the standard treatment response distribution and experimental treatment response prior distribution, respectively. In addition, a 30% toxicity constant rate and beta (0.6, 1.4) priors were assumed for the standard treatment toxicity constant rate and experimental treatment toxicity prior

distribution, respectively.

The probability of stopping the study early if the true ORR of the combination treatment was 30% and the true toxicity rate was 30% was 17.6%. Probabilities of stopping early for high true toxicity rates (i.e., 50%) were 86.5% when the true ORR was 40% and 93.1% when true ORR rate was 25%.

Table 19. Operating characteristics for simultaneous monitoring response and toxicity rates for patients treated with combination treatment

| True Toxicity Rate | True ORR | Prob(stop the trial early) |
|--------------------|-------------|----------------------------|
| 0.10 | 0.25 | 0.4344 |
| | 0.30 | 0.2594 |
| | 0.35 | 0.1429 |
| | 0.40 | 0.0751 |
| | 0.45 | 0.0384 |
| | 0.50 | 0.0194 |
| 0.20 | 0.25 | 0.4399 |
| | 0.30 | 0.2665 |
| | 0.35 | 0.1512 |
| | 0.40 | 0.0840 |
| | 0.45 | 0.0477 |
| | 0.50 | 0.0289 |
| 0.30 | 0.25 | 0.4903 |
| | 0.30 | 0.3326 |
| | 0.35 | 0.2277 |
| | 0.40 | 0.1665 |
| | 0.45 | 0.1335 |
| | 0.50 | 0.1163 |
| 0.40 | 0.25 | 0.6483 |
| | 0.30 | 0.5395 |
| | 0.35 | 0.4671 |
| | 0.40 | 0.4249 |
| | 0.45 | 0.4021 |
| | 0.50 | 0.3902 |
| 0.50 | 0.25 | 0.8554 |
| | 0.30 | 0.8107 |
| | 0.35 | 0.7809 |
| | 0.40 | 0.7636 |
| | 0.45 | 0.7542 |
| | 0.50 | 0.7493 |

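### Arms 1 and 2 frontline: the historical ORR of 18-25% comes from CR-type rates, but the trial's ORR is wider, so the 25% benchmark and the rise to 40% are not shown to be like for like

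*Combined protocol and SAP*

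**What the plan says.** Sections 11.3 B (Arm 1 frontline, closed with 15 patients) and 11.3 D (Arm 2 frontline, N=30) use the same benchmark: "Historical data on similar patients show an ORR of 18-25% [the historical response rate in older newly diagnosed AML". Both cite three hypomethylating-agent trials, at 17.5%, 18% and 27.8%. The regimen "will be considered worthy of further investigation if it elicits an increase in ORR to 40% with acceptable toxicity". For the software, a "25% constant rate, and beta(0.5,1.5) priors were assumed for the standard treatment response distribution" and for the experimental response prior, respectively. The futility rule compares the experimental ORR with the standard ORR plus 0.15.

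Section 2.2 B reports the same three trials with their endpoints:

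- Decitabine: "The CR rate plus CRp was 17.8% with decitabine versus 7.8% with TC". Section 11.3 prints this as 17.5%.
- Azacitidine, 20-30% blasts: "The morphologic CR rate was 18% (10 of 55 patients) in the azacitidine group".
- Azacitidine, more than 30% blasts: "Overall response (CR + CRi) rates were comparable in the azacitidine (27.8%) and CCR (25.1%) arms".

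Section 11.2 defines the ORR for Arms 1 and 2 as CR, CRp, CRi and PR, and then adds "marrow clearance of blasts + hematologic improvement (HI) in platelets, hemoglobin, or ANC within 3 months of treatment initiation". For Arm 3 the same section uses a narrower ORR, without PR or HI, that ends in "CRi (complete remission with incomplete count recovery) + MLFS within 6 months of treatment initiation".

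**The concern.** A rule that asks whether one ORR exceeds another by 15 points needs both to be the same endpoint. Here the historical side is CR, CR+CRp or CR+CRi, and the trial side adds PR, marrow clearance and HI. No section converts one scale to the other or argues that they coincide. The Arm 3 definition shows that the protocol itself uses more than one meaning of ORR.

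Two readings are at stake. One is that an observed ORR near 40% is a 15-point improvement over a hypomethylating agent. The other is that the true-ORR 0.25 row of the operating characteristics describes a regimen that adds nothing to one. Neither can be taken from the plan as it stands.

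**Working it through.** **Inputs.** From 11.3 D: standard rate 0.25, margin 0.15, cut-off 0.99, response prior beta(0.5, 1.5); toxicity limit 0.30, cut-off 0.95, prior beta(0.6, 1.4); looks at 6, 9, ..., 27 and a maximum of 30 patients. From 2.2 B: 17.8%, 18% and 27.8%. From Table 1 of 2.3 D: the control column.

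**Step 1: reproduce the limits.** With x responses in n patients, stop if P(p < 0.40) > 0.99 under beta(0.5+x, 1.5+n-x). At n=6, x=0 gives 0.994 (stop) and x=1 gives 0.924 (continue). At n=27, x=5 gives 0.994 (stop) and x=6 gives 0.981 (continue). The full set is 0, 0, 1, 2, 2, 3, 4, 5, as printed. The toxicity limits are likewise 5, 6, 7, 8, 9, 11, 12, 13.

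**Step 2: reproduce the operating characteristics.** With response and toxicity independent, P(stop early) = 1 - P(never cross futility) x P(never cross toxicity), by exact binomial recursion over the looks. At toxicity 0.10 this gives 0.4344 at ORR 0.25 and 0.0751 at ORR 0.40. All 30 cells of the 11.3 D table match. The arithmetic is sound; the open question is what 0.25 stands for.

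**Step 3: when would 0.25 mean no gain?** If h is the true CR-type rate of a hypomethylating agent, the wider definition, net of offsets, must add exactly 25 - h points:

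- h = 17.8%: 25 - 17.8 = +7.2
- h = 18%: 25 - 18 = +7.0
- h = 21.2%, the simple mean (17.8 + 18 + 27.8)/3: +3.8
- h = 27.8%: -2.8

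**Step 4: what do the documents say about that increment?** In the hypomethylating-agent controls of 2.3 D, PR and HI add (1 + 2)/172 = 1.7 points (exact 95% CI 0.4 to 5.0). These are salvage patients, HI counted only if kept beyond 6 months, and there is no marrow-clearance row. Purely as an illustration, adding 1.7 to the cited rates gives 19.5%, 19.7% and 29.5%, and 22.9% on the mean. These lie on both sides of 25%.

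Several features may pull the trial's ORR down:

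- The 3-month window: 2.3 C gives a median of 3 courses to CR/CRi/HI, range 1-9.
- Dropouts counted as failures in the analysis plan, with up to 24 cycles planned (5.4.1).
- Poor-risk or TP53 patients aged 60 or younger (4.2.1 C).
- Patients already treated for MDS or CMML, who enter as frontline (4.2.2).

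**Step 5: two-sided sensitivity.** Arm 2 frontline, printed limits, P(stop early):

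| True wider ORR | Toxicity 0.10 | Toxicity 0.30 |
|---|---|---|
| 17.8% | 0.745 | 0.770 |
| 19.5% | 0.673 | 0.705 |
| 21.2% | 0.597 | 0.637 |
| 22.9% | 0.523 | 0.570 |
| 25% (printed) | 0.434 | 0.490 |
| 29.5% | 0.274 | 0.346 |
| 30% (printed) | 0.259 | 0.333 |
| 35% (printed) | 0.143 | 0.228 |
| 40% (printed) | 0.075 | 0.167 |

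**The case against.** The plan's defenders have four fair points.

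- The primary analysis estimates ORR with a 95% confidence interval. No test against 25% and no final claim of a 15-point gain is scheduled. This stands, and it limits the point to labelling and reporting. But 11.3 still describes success as an increase to 40% from a stated historical ORR, and readers will use it that way.
- The table labels its rows only by true ORR and is correct under that label. This also stands. A reader might infer that the 0.25 row is wrong, or that it cannot represent no gain. The documents do not support that: with a CR-type rate of 21.2% and a net increment of 3.8 points, it would represent exactly that.
- 25% is the top of the stated range and exceeds two of the three cited rates, so it may already allow for a wider endpoint. It may, but the plan does not say so, and the third cited rate (27.8%) is above it.
- The direction is unsettled. A wider definition alone can only raise a response rate, so a reader might infer that the benchmark is too low and the design too lenient. The downward influences in step 4 prevent that conclusion.

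The most tempting stronger reading uses section 2.5, where 35-48% of azacitidine-treated AML patients had HI or better, a range that contains the 40% target. Those are older studies re-analysed under other criteria. They are not stated to be newly diagnosed patients aged 65 or over, and no 3-month window is given. They signal that definition matters, but they do not supply a replacement benchmark.

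**Conclusion.** The concern holds in a limited form. The 18-25% figure is presented as an ORR but is assembled from three narrower and mutually different rates, and nothing reconciles them with the ORR of Arms 1 and 2. The 25% standard rate and the 15-point rise to 40% are therefore not shown to be like for like, and the 0.25 row is not shown to represent a regimen equal to a hypomethylating agent.

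The size and sign of the discrepancy cannot be determined from the documents. Over true rates from 17.8% to 40%, the early-stop probability at toxicity 0.10 runs from 0.745 to 0.075, so the meaning given to the no-gain rate matters. These figures assume independent response and toxicity and the printed limits. The 21.2% mean is unweighted and serves only as a midpoint. The reach is one 30-patient cohort and the report of the 15 patients in the closed Arm 1 cohort.

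**What to change.** In 11.3 D, and in the report of the closed 11.3 B cohort:

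1. Replace the single historical ORR range by the three rates with their own definitions: CR+CRp 17.8% (decitabine), morphologic CR 18% (azacitidine, 20-30% blasts) and CR+CRi 27.8% (azacitidine, more than 30% blasts). Correct 17.5% to the 17.8% of 2.2 B, and state that none of the three includes PR, marrow clearance or HI.
2. Report, with 95% confidence intervals, CR beside 18%, CR+CRp beside 17.8% and CR+CRi beside 27.8%. Under section 8.1, CRi already contains CRp, so a pooled CR+CRp+CRi rate matches only the last of these.
3. Report the wider ORR with its 95% confidence interval, without describing it as a gain over 25%.
4. For 11.3 D, state that the 0.25 row is not shown to mean no gain over a hypomethylating agent on the wider ORR. Give sensitivity on both sides. At toxicity 0.10 the rows to show are 17.8%, 21.2%, 25%, 30%, 35% and 40%, with the values tabulated in the working.

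The primary endpoint, the 40% target, the futility limits and the sample size do not change. The response components are already assessed under section 8.1. The cost is a wording amendment, which needs sponsor and IRB approval under section 12.0, and a few extra estimates. The downside is a less favourable comparison with wide intervals: 12 of 30, for example, has an exact 95% interval of 22.7% to 59.4%.

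### The early-stopping probabilities stated for the Arm 2 frontline cohort are those of Arm 1 frontline; the cohort's own table gives values 8 to 10 points lower at 50% toxicity

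*Combined protocol and SAP*

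**What the plan says.** Section 11.3 describes the cohort under the title "D. Arm 2 Newly diagnosed older AML (≥ 65 years) cohort (Aza+Nivo+Ipi) (N=30"). Its look schedule reads: "Monitoring for toxicity and futility will not begin until 6 patients have been evaluated, and cohort size for future evaluations is 3". Accrual stops for toxicity if a true grade 3/4 toxicity rate above 30% is "highly probable (i.e., probability >95.0%) for the combination treatment", and for futility if it is "unlikely (i.e., probability < 1%) that ORR rate of the combination treatment is greater than" the standard rate by 15 points. On ORR the section says "The target ORR with the experimental treatment is 40"%.

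The two summary sentences after the boundary tables give three early-stopping probabilities:

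- 17.6% at true ORR 30% and true toxicity 30%.
- At 50% toxicity: "Probabilities of stopping early for high true toxicity rates (i.e., 50%) were 86.5% when the true ORR was 40% and 93.1"% at ORR 25%.

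The operating-characteristics table that follows has different values. Its row for 50% toxicity and ORR 25% reads "0.50 | 0.25 | 0.8554". The entry for 50% toxicity and ORR 40% is 0.7636, and the entry for 30% toxicity and ORR 30% is 0.3326.

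The worked futility example says accrual ceases if there is no response "in the first 8 patients treated".

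**The concern.** The summary and the table describe the same rule for the same cohort, so they cannot both be right. The same two sentences, with the same three numbers, appear in section 11.3 B for Arm 1 frontline. That is a different design, with 40 patients and looks every 4. The futility example with 8 patients also fits Arm 1, where 8 is a scheduled look.

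These sentences are where a reader learns how well the rule guards against excess toxicity in a cohort that adds ipilimumab to nivolumab. If they are wrong, an IRB or medical monitor relying on them would credit the rule with more protection than it gives. They would also believe that the two frontline cohorts, which section 3.1 describes as enrolled alternately under these rules, are equally well guarded.

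**Working it through.** **Inputs, all from section 11.3 D**

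- Looks at n = 6, 9, 12, 15, 18, 21, 24, 27; maximum 30.
- Toxicity boundaries (Table 18): stop at or above 5, 6, 7, 8, 9, 11, 12, 13.
- Futility boundaries (first Table 19): stop at or below 0, 0, 1, 2, 2, 3, 4, 5.
- Priors: beta(0.5, 1.5) for response and beta(0.6, 1.4) for toxicity. The constant historical ORR is 25%, so the futility threshold is 0.25 + 0.15 = 0.40. The toxicity limit is 0.30. Posterior cut-offs are 0.99 and 0.95.

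**Step 1: boundaries.** At each look, the futility boundary is the largest x with Pr(p < 0.40 | beta(0.5 + x, 1.5 + n − x)) > 0.99. The toxicity boundary is the smallest x with Pr(p > 0.30 | beta(0.6 + x, 1.4 + n − x)) > 0.95. Every printed boundary from n = 6 to 27 is recovered. For example, 0 responses in 6 gives Pr(p < 0.40 | beta(0.5, 7.5)) = 0.9936, so futility is crossed at 6.

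**Step 2: operating characteristics.** With response and toxicity independent,

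P(stop early) = 1 − P(toxicity boundary never crossed) × P(futility boundary never crossed),

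where each factor comes from exact binomial enumeration over the looks.

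- P(toxicity never crossed): 0.9010 at 30% toxicity; 0.2556 at 50%.
- P(futility never crossed): 0.5657 at ORR 25%; 0.7408 at ORR 30%; 0.9251 at ORR 40%.

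| Toxicity / ORR | Calculation | Result | Arm 2 table | Arm 2 text | Text minus table |
|---|---|---|---|---|---|
| 50% / 40% | 1 − 0.2556 × 0.9251 | 0.7636 | 0.7636 | 86.5% | +10.1 points |
| 50% / 25% | 1 − 0.2556 × 0.5657 | 0.8554 | 0.8554 | 93.1% | +7.6 points |
| 30% / 30% | 1 − 0.9010 × 0.7408 | 0.3326 | 0.3326 | 17.6% | −15.7 points |
| 30% / 40% | 1 − 0.9010 × 0.9251 | 0.1665 | 0.1665 | not stated | – |

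All 30 cells of the table reproduce to four decimals.

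**Step 3: can any reading of the Arm 2 rule give the text's figures?** Adding a toxicity look at n = 3, or dropping the futility look at n = 6, moves the 50% / 40% value only between 0.756 and 0.770, and the 50% / 25% value only between 0.846 and 0.860. Neither reaches 0.865 or 0.931.

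**Step 4: where the figures come from.** The same method with the Arm 1 frontline boundaries (Tables 12 and 13, looks at 4 to 36) gives 0.8646 (50% / 40%), 0.9309 (50% / 25%) and 0.1759 (30% / 40%). These equal Table 14 and round to the three numbers in the Arm 2 text. The 0.1759 is at ORR 40%. Table 14 has no ORR 30% row, and the Arm 1 boundaries at ORR 30% and toxicity 30% give 0.378. The Arm 1 sentence therefore mislabels this value, and the Arm 2 sentence repeats the mislabel.

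**Step 5: the futility example.** Looks fall at 6 and 9, not 8. Table 19 sets a boundary of 0 for n = 6 to 9, so zero responses in 6 already stops accrual.

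**The case against.** The strongest reply is that only descriptive prose is wrong. The decision rules, priors and boundary tables agree with one another, and the correct probabilities are printed immediately below the faulty sentence. That stands: no boundary, sample size or decision changes.

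Four narrower points also have weight:

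- The gap between 17.6% and 33.3% is largely a labelling error. At the target ORR of 40% the Arm 2 value is 16.7%, only 0.9 points from 17.6%. The sentence as written still says 30%, and is wrong for that case.
- The futility example says accrual ceases at 0 of 8; it does not say accrual continues at 0 of 6. Table 19 governs, so the example is misleading but does not override the rule.
- These probabilities combine toxicity and futility stops. The toxicity rule alone stops in 1 − 0.2556 = 74.4% of trials at 50% toxicity, whatever the ORR. The ORR 25% figures in particular include many futility stops.
- The reporting text at the end of section 11.3 asks for summaries every 5 evaluable patients, and section 5.2.2.6 has safety monitoring every 5 patients. If looks fell every 5 with the same priors and cut-offs, the values at 50% toxicity would be about 74.8% (ORR 40%) and 82.4% (ORR 25%). That is further from the text, not closer.

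That the sentences were carried over from Arm 1 is an inference, though identical wording and three matching numbers leave little room for another explanation.

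**Conclusion.** The point holds. The Arm 2 frontline text contradicts its own table, and the table is correct. At 50% true toxicity and the 40% target ORR, the chance that the cohort is not stopped early is 23.6% (100 − 76.4), not the 13.5% (100 − 86.5) the text implies. At ORR 25% it is 14.5% (100 − 85.5) rather than 6.9% (100 − 93.1). At ORR 30% and toxicity 30% the stated stopping probability is about half the table's value.

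This rests on the printed look schedule and boundaries and on independence of response and toxicity; the exact match with the sponsor's table supports both. It is an error in the reported performance of the rule, together with a worked example that does not fit the schedule. It is not a fault in the boundaries, and it should be corrected because the summary claims a property the cohort does not have.

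**What to change.** In section 11.3 D, replace the two summary sentences with the table's values. The probability of stopping early is 16.7% at true ORR 40% and toxicity 30% (33.3% at ORR 30%). At 50% toxicity it is 76.4% at ORR 40% and 85.5% at ORR 25%. State that these combine futility and toxicity stops.

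Change the futility example to no response in the first 6 patients, in line with Table 19. In section 11.3 B, relabel the 17.6% as the value at ORR 40%. Give the Arm 2 operating-characteristics table its own number, since Table 19 is currently used for both it and the futility boundaries.

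The cost is a text correction. Every replacement figure is already in the plan, so no new simulation or redesign is needed. The stated performance at 50% toxicity becomes less favourable.
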